4.2. Rationale

The current trial is an open-label extension trial to the Phase 3 IMPALA trial (MOL-PAP-002) to allow patients to continue treatment with inhaled molgramostim nebuliser solution, and to investigate long term safety and efficacy of inhaled molgramostim nebuliser solution in aPAP patients. The trial consists of an up to 36-month treatment period during which patients will receive the same dose regimen of inhaled molgramostim nebuliser solution as was used in the Follow-up Period of the IMPALA trial (cycles of seven days molgramostim 300 µg administered once daily, and seven days off treatment). The patient population to be included in the current trial will be patients with aPAP who have completed the IMPALA trial.

The primary objective is safety assessed by AE reporting. In addition to clinical signs and symptoms, clinically significant changes in laboratory parameters (haematology and clinical chemistry) and electrocardiogram (ECG) variables will be reported as AEs. In order to characterize potential systemic adverse effects, GM-CSF levels before dosing and at T_{max} (2 hours) will be assessed in a subset of subjects, i.e. subjects enrolled at the trial site in Italy.

Long term efficacy will also be assessed using (A-a)DO₂, as a secondary endpoint, which has been found to be sensitive to treatment with inhaled rhGM-CSF with a low degree of variability in previous literature. In a phase II trial the statistically significant improvement in (A-a)DO₂ was accompanied by statistically significant improvements in dyspnoea, need for oxygen supplement, walking distance and minimal oxygen saturation (SpO₂) on the 6MWT, VC and DLCO [Tazawa 2010]. Improvements were also associated with morphologic changes as evidenced by statistically significant correlations between high-resolution CT scores and (A-a)DO₂, PaO₂ and DLCO both before and after treatment.

Whilst (A-a)DO₂ is a calculated biomarker, other secondary endpoints focus on important direct clinical outcomes such as the need for WLL and the effect of treatment on exercise capacity, and QoL. Currently WLL is the standard of care for aPAP patients but the procedure is invasive, and carries a known morbidity to the patient. Potential complications associated with WLL include hypoxaemia, hydropneumothorax, adult respiratory disease syndrome, post-procedure infections and pneumothorax [Leth 2013]. Therefore, a reduced requirement for WLL would be of benefit for the patient. As the main symptom of aPAP is exercise-induced dyspnoea that may limit the activity level of the patient, the 6-minute walking distance (6MWD) and the total score on the St Georges Respiratory Questionnaire (SGRQ) were chosen as secondary endpoints, although data on these endpoints in aPAP are still limited. In addition, pulmonary function, PaO₂ and disease severity, need for oxygen supplement therapy, and number of subjects not requiring treatment and the time off treatment after discontinuation will be assessed as secondary endpoints.

4.3. Potential Risks and Benefits

Currently, no evidence-based curative treatment exists for aPAP. Successive WLL procedures remain the standard treatment without a targeted pathophysiological

approach. WLL is an intervention which carries a high morbidity, treats only symptoms, and is not always successful. Due to the pathophysiology of aPAP, this condition can lead to complications, including respiratory infections, pulmonary fibrosis and potentially premature death.

There is currently no approved pharmacological treatment for patients with PAP, and therefore an unmet need for further treatment modalities exists.

Experience with inhaled rhGM-CSF worldwide has demonstrated a reduction in symptoms and improvement in exercise tolerance and objective lung function tests, reducing or eliminating further WLL episodes. Thus treatment with rhGM-CSF has the potential to alter the natural history of PAP [[Seymour 2002](#), [Luisetti 2010](#)].

Clinical studies and case reports thus far have indicated the use of inhaled rhGM-CSF to be a well-tolerated, effective and localised treatment that may offer clinical benefits for the great majority of patients, including clearance of excess surfactant-related lipoproteins and prevention of secondary infections [[Ohashi 2012](#), [Leth 2013](#)].

Patients with aPAP have been treated with up to 500 µg/day of inhaled rhGM-CSF for up to 68 months without chronic toxic effects [[Papiris 2014](#), [Wylam 2006](#)]. Results from pre-clinical studies with inhaled molgramostim nebuliser solution showed the expected pharmacological effects on WBC populations locally and systemically in line with observed effects after intravenous administration of molgramostim. No severe, serious or dose-limiting AEs were observed in the first clinical trial in humans (MOL-001). The most common AE was cough, which was reported at a similar incidence for molgramostim nebuliser solution and placebo. Increases of WBC populations in the blood consistent with the known mechanism of action were observed; most of which were considered not clinically significant. Only two cases (total white blood cell increased and eosinophilia) were reported as AEs. No development of anti-drug antibodies was observed. In the ongoing IMPALA trial in patients with aPAP, three reviews of unblinded safety data by an independent DSMB have not identified safety signals of concern and the DSMB recommended that the trial could continue as planned.

Based on information from similar products, the potential dose-limiting toxicity of molgramostim would be based on pulmonary effects, such as bronchoconstriction, dyspnoea, cough or decreased pulmonary function. Pulmonary function and respiratory symptoms will be monitored during the trial and treatment should be discontinued if significant worsening occurs. If there is significant systemic exposure, haematologic findings such as leukocytosis and neutrophilia may occur. As non-clinical data indicate that systemic exposure to rhGM-CSF may be associated with increased pre- and post-implantation losses, pregnancy testing will be performed in women of childbearing potential at each trial visit where molgramostim is dispensed and at home at monthly intervals during treatment.

Treatment with molgramostim nebuliser solution is expected to be more effective, less invasive, and more convenient, than the currently available symptomatic treatment, WLL, for patients with aPAP.

5. TRIAL OBJECTIVES AND PURPOSE

5.1. Primary Objective

The primary objective is to investigate safety of long term use of inhaled molgramostim.

5.2. Secondary Objectives

The secondary objectives are

- To investigate effects of long term use of inhaled molgramostim on oxygenation.
- To investigate effects of long term use of inhaled molgramostim on exercise capacity.
- To investigate effects of long term use of inhaled molgramostim on respiratory quality of life.
- To investigate requirement for WLL during long term use of inhaled molgramostim.
- To investigate effects of long term use of inhaled molgramostim on lung function.
- To investigate maintenance of effect after discontinuation of inhaled molgramostim.

5.3. Study Endpoints

5.3.1. Primary Endpoints

Number of AEs, SAEs, adverse drug reactions (ADRs), and AEs leading to treatment discontinuation.

5.3.2. Secondary Endpoints

- (A-a)DO₂ during the trial
- 6MWD during the trial
- SGRQ total score during the trial
- Frequency of WLL during the trial
- DLCO (% predicted), FEV₁ (% predicted), and FVC (% predicted) during the trial
- PaO₂ and disease severity score (DSS) during the trial
- Need for oxygen supplement therapy during the trial
- Number of subjects not requiring treatment for aPAP and time off treatment after discontinuation of inhaled molgramostim

5.3.3. Exploratory Endpoints

- GM-CSF levels before and 2 hours after dosing

6. INVESTIGATIONAL PLAN

6.1. Overall Study Design

Subjects with aPAP who have completed the IMPALA (MOL-PAP-002) trial will be eligible for this trial.

At the Baseline visit, eligible subjects may continue or re-start treatment with inhaled molgramostim (300 µg) administered intermittently in cycles of seven days molgramostim, administered once daily, and seven days off treatment.

Trial visits will be conducted at 6-monthly intervals until the end of trial. Participating subjects will be encouraged to contact the clinic between visits if they experience AEs or worsening of aPAP, or if they have any other concerns.

During the trial, WLL will be applied as rescue therapy. The criterion for performing WLL is clinical worsening of aPAP based on symptoms, reduced exercise capacity and/or findings of hypoxemia or desaturation according to the investigator's judgement. The reason(s) for conducting WLL will be documented. Subjects undergoing WLL will continue treatment with molgramostim, unless discontinuation is medically required, according to investigator's discretion.

Subjects may discontinue molgramostim due to remission of aPAP, lack of response that requires a different treatment modality, or AEs. Subjects becoming pregnant will be required to discontinue treatment with molgramostim. Subjects who discontinue molgramostim will continue in the trial and attend visits according to the same schedule until end of the trial. Molgramostim treatment may be re-started if medically required. Subjects not requiring treatment at the Baseline visit may start molgramostim treatment during the trial if medically required.

6.1.1. Trial Period

The first patient will be included in the trial in Q1 2018 and the expected end of trial is in Q1 2021. Should the product not have obtained marketing authorization at this date, the trial will be amended with an extension of one year at a time to ensure adequate treatment options for subjects in the trial who still are in need of treatment with inhaled molgramostim. Trial completion, defined as the date of the Clinical Trial Report, is expected 1 year after trial end.

6.1.2. End of Trial

The end of trial is defined as the last subject's last visit.

6.2. Number of Subjects

Up to 90 subjects may be included.

6.3. Treatment Assignment

All subjects in need of treatment will receive inhaled molgramostim.

6.4. Dose Adjustment Criteria

6.4.1. Safety Criteria for Adjustment or Stopping Doses

Not applicable.

6.4.2. Pharmacokinetic Criteria for Adjustment or Stopping Doses

Not applicable.

6.5. Criteria for Study Termination

The investigator or the sponsor may terminate this trial prematurely for any reasonable cause. The Independent Ethics Committees (IECs)/Institutional Review Boards (IRBs) and Competent Authorities should be informed promptly.

Conditions that may warrant termination include, but are not limited to:

- The discovery of an unexpected, significant, or unacceptable risk to the subjects enrolled in the trial, or potential trial subjects.
- A decision on the part of the sponsor to suspend or discontinue development of the IMP.
- Marketing approval of molgramostim nebuliser solution.

If the Competent Authority obtains information that raises doubts about the safety or scientific validity of the clinical trial, the Competent Authority can suspend or prohibit the trial. Before the Competent Authority reaches its decision, it shall, except where there is imminent risk, ask the sponsor and/or the investigator for their opinion, to be delivered within one week (Directive 2001/20/EC, Article 12, Section 1).

If the trial is prematurely terminated or suspended for any reason, the investigator/institution should promptly inform the trial subjects and should assure appropriate therapy and follow-up for the subjects.

7. SELECTION AND WITHDRAWAL OF SUBJECTS

7.1. Subject Inclusion Criteria

1. Completer of the IMPALA trial.
2. Females who have been post-menopausal for >1 year, or females of childbearing potential after a confirmed menstrual period using a highly efficient method of contraception (i.e. a method with <1% failure rate such as combined hormonal contraception, progesterone-only hormonal contraception where inhibition of ovulation is the primary mode of action, intrauterine device, intrauterine hormone-releasing system, bilateral tubal occlusion, vasectomised partner, sexual abstinence*), during and until 30 days after last dose of trial treatment. Females of childbearing potential must have a negative urine pregnancy test at Baseline or at start of treatment if treatment is not dispensed at Baseline, and must not be lactating during and until 30 days after last dose of trial treatment.
3. Males agreeing to use condoms during and until 30 days after last dose of trial treatment, or males having a female partner who is using adequate contraception as described above.
4. Willing and able to provide signed informed consent.

* Vasectomised partner is a highly effective birth control method provided that partner is the sole sexual partner of the female trial participant of child bearing potential and that the vasectomised partner has received medical assessment of the surgical success. Sexual abstinence is considered a highly effective method only if defined as refraining from heterosexual intercourse during the entire period of risk associated with the study treatments. The reliability of sexual abstinence needs to be evaluated in relation to the duration of the clinical trial and the preferred and usual lifestyle of the subject. [[CTFG 2014](#)]

7.2. Subject Exclusion Criteria

1. Treatment with GM-CSF products other than molgramostim nebuliser solution within three months of Baseline.
2. Treatment with any IMP other than inhaled molgramostim within four weeks of Baseline.
3. History of allergic reactions to GM-CSF.
4. Connective tissue disease, inflammatory bowel disease or other autoimmune disorder requiring treatment associated with significant immunosuppression, e.g. more than 10 mg/day systemic prednisolone.
5. Previous experience of severe and unexplained side-effects during aerosol delivery of any kind of medicinal product.
6. History of, or present, myeloproliferative disease or leukaemia.
7. Apparent pre-existing concurrent pulmonary fibrosis.
8. Any other serious medical condition which in the opinion of the investigator would make the subject unsuitable for the trial.

7.3. Subject Withdrawal Criteria

7.3.1. Discontinuation of Trial Treatment

Subjects may be discontinued from treatment and assessments at any time, if deemed necessary by the investigator. Potential reasons for discontinuation of treatment are:

- Remission of aPAP
- Lack of efficacy/worsening of disease (e.g. loss of response that requires a different treatment modality).
- Unacceptable AE (including serious hypersensitivity reaction).
- Pregnancy.

Those who discontinue treatment will not automatically be withdrawn from the trial but will be encouraged to continue to follow the same visit schedule. If medically indicated and no safety-related exclusion criteria have emerged, treatment may be restarted at a later visit.

The reason and date the subject is discontinued will be documented in the electronic case report form (eCRF).

Subjects who fulfil the criteria for rescue treatment will be scheduled for a WLL as described in Section 10.2. Subjects receiving a WLL should continue treatment and attend the remaining visits, unless discontinuation is medically required, according to investigator's discretion.

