- ^d Only applicable if assessment is done according to clinical practice or medical need, e.g. in case of a clinical deterioration. If done, results will be recorded
- ^e Capillary sampling for blood gas analysis may be used instead of an arterial blood gas sample at sites that routinely use this method.
- ^f DLCO, FEV₁, and FVC (absolute values and % of predicted values).
- ^g 6MWT includes assessment of SpO₂ and Borg CR10 score for dyspnoea before, during (SpO₂) and after (Borg) the test. If the subjects used supplemental O₂ during the procedure in IMPALA, the same O₂ flow will be used at the subsequent tests in this trial, if possible.
- ^h Haematology and clinical chemistry
- ⁱ For Italy only: Patients will have their visits scheduled for an on-treatment week within the allowed window of +/- 4 weeks. The first sample must be taken just prior to inhalation of molgramostim. The 2nd sample must be taken 2 hours post dosing, (+/- 10 minutes). See Section [10.8.5.1](#)
- ^j Trial drug is dispensed to subjects who require treatment according to investigator's discretion. **For Italy only:** The visit should take place in during the week on treatment. On the day of dosing, the subjects will do the nebulization at the clinic, in order to collect pre-dose PK sample.
- ^k Diary card to collect safety information to be given to the subject and collected at the next visit. The subject will be asked to record any AEs they have experienced, enter dates for pregnancy tests taken at home (if applicable) and dates for changing of the nebuliser mouthpiece in the subject diary.
- ^l If the planned trial termination has been declared since the subject's last visit in the trial, the subject will leave the trial.

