Pre-clinical studies in cynomolgus monkeys show that molgramostim nebuliser solution is well tolerated locally and that it has low systemic toxicity. The small fraction of the inhaled dose that is absorbed systemically causes increases in stem cell proliferation, resulting in increased number of monocytes, eosinophils and neutrophils in the circulation; similar to the known effects after intravenous administration of rhGM-CSF. Local effects in the lungs are characterised by accumulation of inflammatory cells, mostly macrophages, accompanied by an increased cellularity in the lymphoid tissue that is associated with the respiratory tract and minimal to mild exudation of red blood cells (RBC) into the alveoli. The infiltration of inflammatory cells was not associated with any signs of inflammation or impaired lung function, and it is interpreted as an exaggerated pharmacological effect of molgramostim. Its severity was graded slight at the 10 µg/kg/day dose level and moderate above this level. Duration of treatment did not affect the severity of this finding. Reduced severity of the lung and tracheobronchial changes following 4 weeks off dose in recovery animals suggests partial resolution of the changes.

An embryo-foetal developmental (EFD) toxicity trial in rabbits revealed increases in post implantation loss, decreases in the number of live implants, effects on sex ratio and a slight increase in the incidence of major malformations in foetuses at the highest dose (150 µg/kg/day). Studies in sexually mature monkeys have shown that molgramostim has no effect on male and female reproductive organs. Further details are available in the IB. The nonclinical data raises a concern about human teratogenicity/fetotoxicity in early pregnancy, risk mitigation measures (contraception and pregnancy testing) have therefore been implemented in the trial.

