10.9.3.5. Pregnancy

Female subjects will be instructed to notify the investigator immediately if they become pregnant during the trial. Male subjects will be instructed to notify the investigator immediately if their female partner becomes pregnant. Pregnant subjects will be withdrawn from further trial treatment. The subjects will also be instructed to report pregnancies discovered after the last visit, if they believe that conception occurred during their participation in the trial.

A pregnancy as such is not an AE, unless there is a possibility that the IMP has interfered with the efficiency of any contraceptive measures. However, the investigator should report pregnancies according to the procedures and timelines described for reporting of SAEs, Section 10.9.3.1. The pregnancy report form should be used instead of the SAE form.

The pregnant subject or partner will be followed until the end of the pregnancy. Any complication during the pregnancy should preferably be reported as an AE. The outcome of the pregnancy must be reported on the pregnancy report form. Any spontaneous abortion, stillbirth, birth defect/congenital anomaly, death, or other serious infant condition must be reported and followed up as an SAE.

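### The protocol's pregnancy safeguards disagree on unscheduled dispensing, off-drug testing, re-starts and reporting after the last dose, and need to be reconciled

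*Protocol*

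**What the plan says.** - **Reason for the measures (Protocol 4.1).** "The nonclinical data raises a concern about human teratogenicity/fetotoxicity in early pregnancy, risk mitigation measures (contraception and pregnancy testing) have therefore been implemented".
- **Period (Protocol 7.1).** Inclusion criterion 2 requires contraception "during and until 30 days after last dose of trial treatment", and women "must not be lactating during and until 30 days after last dose of trial treatment". Criterion 3 applies the same 30 days to male subjects. Women of childbearing potential "must have a negative urine pregnancy test at Baseline or at start of treatment if treatment is not dispensed at Baseline".
- **Testing at dispensing (Protocol 4.3).** "pregnancy testing will be performed in women of childbearing potential at each trial visit where molgramostim is dispensed", with monthly home tests during treatment.
- **Flow chart (Protocol Table 1, repeated in SAP 3.2).** The pregnancy test and contraceptive check are marked for Visits 1 to 7. In the Unscheduled column, that row and the drug-dispensing row both carry note d: "Only applicable if assessment is done according to clinical practice or medical need". Note c makes tests optional for women off drug. It ties the urine test, whose purpose is immediate confirmation, to Baseline or the first dispensing visit.
- **Pregnancy screen (Protocol 10.8.5.2).** Women of childbearing potential have a serum test at each visit, with no restriction to women on drug.
- **Re-start (Protocol 7.3.1).** "If medically indicated and no safety-related exclusion criteria have emerged, treatment may be restarted at a later visit".
- **Reporting (Protocol 10.9.3.5 and 10.9.3.1).** Pregnant subjects stop trial drug. Pregnancies discovered after the last visit are to be reported by subjects "if they believe that conception occurred during their participation in the trial". The investigator follows the SAE procedures and timelines, which run to Day 30 after the last visit.
- **Last planned contact.** Section 10.6 puts the follow-up call about one week after the last visit. Table 1 puts it at two weeks with a one-week window.

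**The concern.** Contraception and testing are the protocol's stated means of controlling a stated foetal risk, so the passages that put them into effect should give a site one answer. They do not. A site dispensing at an unscheduled visit, seeing a woman who is off drug, or re-starting a woman after a break can follow one section and depart from another. After the trial, a pregnancy conceived inside the protocol's own 30-day period may never reach the site, because the subject's reporting instruction is tied to participation and not to the last dose. Safety is the primary objective, and the protocol follows each reported pregnancy to its end. An unreported one is therefore lost safety information. No sample size, analysis or planned table depends on the point.

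**Working it through.** The documents give no figure to reproduce. The check compares passages and does calendar arithmetic.

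**(a) Unscheduled dispensing.** Under note d, dispensing and the pregnancy check are each conditional on clinical practice or medical need, and neither is conditional on the other. Table 1 therefore permits dispensing with no test. Section 4.3 says testing is done wherever drug is dispensed. The two conflict.

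**(b) Testing off drug.** Note c makes it optional; 10.8.5.2 includes it at each visit. The two conflict. They also differ on the Baseline urine test: 10.8.5.2 names it for women with a gap after IMPALA, while note c and criterion 2 have no such limit.

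**(c) Re-start.** Section 7.3.1 looks only to exclusion criteria. None of the eight in Section 7.2 mentions pregnancy, lactation or contraception; these are in inclusion criteria 2 and 3. The immediate urine test is named for Baseline or first dispensing, not for a re-start, and Table 1 has no row for lactation. On the other side, a re-start at a planned visit falls on a visit with a scheduled test and contraceptive check. What is missing is any passage that makes a negative result, contraception and non-lactation a condition of the re-start dose.

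**(d) After the last dose.** Inputs: 30 days (7.1); call at 7 days (10.6), or 14 to 21 days (Table 1, taking its trial completion to mean the subject's last visit); 26-week kit with 13 weeks of dosing (9.2); 7 days on, 7 off (6.1).

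Kit length: 26 × 7 = 182 days. Dosing days: 13 × 7 = 91. If a cycle starts on the day of Visit 6 (day 0), the last dosing day is 12 × 14 + 6 = 174, which is 182 − 174 = 8 days before an on-time Visit 7. If the visit falls in a dosing week, the last dose can be on the visit day (0 days before).

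Days of the period left after the call = 30 − (days from last dose to last visit) − (days from last visit to call):

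| Last dose before last visit | Call at 7 days | Call at 14 days | Call at 21 days |
|---|---|---|---|
| 0 days | 30 − 0 − 7 = 23 | 30 − 0 − 14 = 16 | 30 − 0 − 21 = 9 |
| 8 days | 30 − 8 − 7 = 15 | 30 − 8 − 14 = 8 | 30 − 8 − 21 = 1 |

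A late visit with the kit used up shrinks this. One week late (day 189), the last dose is 189 − 174 = 15 days back, leaving 8, 1 or no days. Four weeks late (day 210), it is 36 days back and the period is already over.

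The table treats participation as lasting until the call. If it ends at the last visit, 30 − 8 = 22 to 30 − 0 = 30 days lie outside the subject's instruction.

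**Does the Day 30 window close this?** By calendar date it does: with the last dose at or before the last visit, Day 30 after that visit is no earlier than 30 days after the last dose. It works only if the site hears in time. If Day 30 limits when the site learns of the pregnancy, and recognition lags conception by 1 to 6 weeks (an assumption; the documents give no figure), conception must fall by Day 30 − 7 = 23 or Day 30 − 42 = −12. With the last dose on the visit day, between 7 and all 30 of the days would then be recognised too late. If Day 30 refers instead to the date of conception, the investigator's duty spans the period, but it still depends on a subject who was not told to report.

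**The case against.** The strongest reply is that 7.3.1 should not be read alone. Table 1 schedules a test and contraceptive check at every planned visit, note c waives only the test, 4.3 and 10.8.5.2 call for a test where drug is dispensed, and 10.9.3.5 takes pregnant subjects off drug. This stands, and it limits the re-start part to a missing link. A reader might infer that a woman can be re-started with no check at all, or that the plan allows exposed pregnancies to begin. The documents do not support that.

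A reader might also infer that a re-starter's contraception duty lapsed many months earlier. That depends on what last dose means when treatment stops and resumes, which the protocol does not define, so no duration can be attached.

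On reporting, it is fair to say that the Day 30 window spans the dates and that SAEs judged related are reportable at any time. Neither brings in an uncomplicated pregnancy the site never hears of. The follow-up call is described as covering AEs, and 10.9.3.5 says a pregnancy is not in itself an AE. It would also go too far to call conceptions late in the 30 days drug-exposed: 4.1 reports a half-life of approximately 4 hours in healthy adults. The 30 days is used here only because it is the protocol's own period.

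Finally, note d is a general footnote on most rows of its column, and a site may well follow the more specific 4.3. That makes harm less likely but leaves the conflict in place.

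**Conclusion.** The concern holds as a set of inconsistencies. Two are direct conflicts: note d against 4.3 on unscheduled dispensing, and note c against 10.8.5.2 on testing off drug. One is a missing link: 7.3.1 does not refer to inclusion criteria 2 and 3. One is a partial gap: the subject's reporting scope in 10.9.3.5 is narrower than the 30-day period, and the Day 30 investigator window makes up for it only if the subject reports in time.

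Of the 30 days, 9 to 23 fall after the follow-up call if the last dose is on the day of the last visit, and 1 to 15 if it is 8 days earlier. Fewer or none remain if that visit is late and the kit is used up. These figures assume dosing to the schedule. SAP 3.2 has 55 of 60 subjects on treatment at termination, so dosing close to the final visit is plausible for many, but 55 is not a count of people at risk. The numbers of childbearing potential and of re-starts are not given, so the number of pregnancies affected cannot be estimated. The point should be corrected because it concerns subject safety and the remedy is wording.

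**What to change.** Reconcile 7.3.1, Table 1 notes c and d, 4.3 and 10.8.5.2 with inclusion criteria 2 and 3, so that one consistent statement covers first starts, re-starts and unscheduled dispensing. State what last dose means when treatment is interrupted. Reconcile the reporting scope in 10.9.3.5, for subjects and for partners of male subjects, and the timing of the follow-up call (10.6 against Table 1), with the protocol's own period of 30 days after the last dose. Which testing or contraception rule applies is for the sponsor and its clinical advisers; the request is that the sections agree.

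The cost is amendment wording, with the subject information updated to match, and possibly a few more pregnancy reports to follow. No visit is added and no analysis changes. SAP 3.2 records that the trial is closing early. If an amendment can no longer take effect, the trial report should state over what period pregnancies were collected.
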